11.2 Study Hypotheses

This Phase II study is not designed to test a formal null hypothesis. Rather, it is intended to obtain sufficient data to obtain meaningful estimates of the immune response induced when 2017 H7N9 IIV is administered sequentially or simultaneously (within 15 minutes) with licensed seasonal influenza vaccine, and to uncover any safety issues that occur at a sufficiently high rate that they might be observed in a study of this size. The sample size facilitates formal testing of selected hypotheses as discussed in [Section 11.4.3](#), along with the probability of observing safety outcomes and the precision of immunogenicity outcomes.

11.3 Study Outcome Measures

Please refer to study outcome measures in [Section 3.2](#).

11.4 Sample Size Considerations

Please refer to study design outlined in [Section 4.0](#).

11.4.1 Study Population

The study population for this clinical trial includes males and non-pregnant females, 19-64 years of age, who are in good health and meet all eligibility criteria. The subjects will be recruited from the general population at the participating VTEU sites that have substantial experience conducting large influenza vaccine studies.

11.4.2 Subject Enrollment and Follow-up

Based on the accrual rates observed in similar studies, it seems reasonable to expect that the participating VTEUs will be able to enroll this trial in a timely fashion. In previous DMID trials of A/H7N9 vaccines, 5 VTEUs recruited 975 healthy adults, ages 19-64 in 10 weeks. Prior experience suggests up to 15% of subjects may be excluded from the per protocol analysis for post dose 3 assessments, either because they did not receive the second or third study vaccinations, were lost-to-follow-up, or because they had a protocol deviation requiring their exclusion from the per protocol analysis.

A total of N=60 in Groups 1-2, and N = 30 in Group 3 will be enrolled and randomized. Assuming up to 15% drop out by Day 64, this will ensure at least N=50 in Groups 1-2 and N=25 in Group 3 are available for the primary immunogenicity analysis.

Follow-up will consist of 2 segments. The first encompasses the core data for this trial and will consist of results for all study visits through approximately 21 days after the last study vaccination. The second segment consists of a 6-month immunogenicity assessment and follow-up safety assessments through approximately 12 months after the last study vaccination.

11.4.3 Sample Size

This study is planned to enroll a minimum of 60 subjects in Groups 1-2, and 30 subjects in Group 3. This study is not designed to test a formal null hypothesis. Rather, it is intended to obtain sufficient data to obtain meaningful estimates of the immune response and to uncover any safety issues that occur at a sufficiently high rate that they might be observed in a study of this size. As such, the type one error rate, alpha = 0.05, is not adjusted for multiple comparisons.

While this study is not designed to test any specific null hypothesis, the following tables illustrate the precision and power for select estimates and comparisons of interest.

[Table 3](#) indicates the probability of observing one or more safety events, such as solicited injection site or systemic reactogenicity events or an unsolicited non-serious AE of a particular type for a single treatment arm (N = 30 or 60), and for all subjects receiving AS03-adjuvanted 2017 H7N9 IIV (N = 120).

Table 3: Power (%) to Detect Safety Events:

Event Frequency	N = 30	N = 60	N = 120
≥10% Very Common	96	>99	>99
≥1%	26	45	70

Common			
$\geq 0.1\%$ Uncommon	3	6	11
$\geq 0.01\%$ Rare	<1	<1	1

Binomial confidence intervals (CI) are widest (have the least precision) when the response rate is 50%. [Table 4](#) is presented to indicate the worst-case scenario for precision of observed exact (Clopper-Pearson) binomial confidence intervals.

Table 4: Precision of Binomial Confidence Intervals:

N	95% CI
30	31-69
60	37-63
120	40-60

For each of the primary immunogenicity objective, a power analysis is provided below for testing the following hypotheses with the planned sample size, where p_c = proportion responders in comparator arm; p_e = proportion responders in experimental arm.

Test for difference in proportion responders:

$H_0: p_c - p_e = 0$ – No difference in proportion responders

$H_1: p_c - p_e \neq 0$ – difference in response rates

[Table 5](#) and [Table 6](#) present the minimum detectable differences in the proportion of subjects responding (e.g., attaining seroconversion or a titer $\geq 1:40$) between two treatment arms using a two-sided Likelihood Ratio Test and alpha = 0.05.

Primary Immunogenicity Objective 1: Evaluate antibody responses against A/H7N9 at approximately 21 days following receipt of two doses of AS03-adjuvanted 2017 H7N9 IIV. Comparison between simultaneous and sequential receipt to IIV4, i.e., Group 1 at Day 43 vs. Group 2 at Day 64.

Table 5: Objective 1 -Minimum Detectable Difference in Proportion Responders with 80% Power (N = 50 per group)

Assumed Proportion Responders comparator arm (p_c)	Minimum detectable difference in response rate ($p_c - p_e$)
0.50	0.27

Assumed Proportion Responders comparator arm (p_c)	Minimum detectable difference in response rate ($p_c - p_e$)
0.60	0.27
0.70	0.27
0.80	0.26
0.90	0.22

Primary Immunogenicity Objective 2: Evaluate antibody responses against the seasonal influenza strains at approximately 21 days following receipt of IIV4.

Comparator Group (N = 75):

- Group 2 (IIV4/H7N9/H7N9) + Group 3 (IIV4) at Day 22

Experimental Groups (N = 50/group):

- Group 1 (H7N9+IIV4/H7N9) at Day 64

Table 6: Objective 2 - Minimum Detectable Difference in Proportion Responders with 80% Power

Assumed Proportion Responders comparator arm (p_c)	Minimum detectable decrease in response rate ($p_c - p_e$)
0.40	0.23
0.50	0.24
0.60	0.25
0.70	0.25
0.80	0.23
0.90	0.20

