9.7.1 Sample Size

Table 8: Power (%) to Detect Safety Events

Event Frequency	N = 30	N = 60	N = 120
$\geq 10\%$ Very Common	96	>99	>99
$\geq 1\%$ Common	26	45	70
$\geq 0.1\%$ Uncommon	3	6	11
$\geq 0.01\%$ Rare	<1	<1	1

Table 9: Precisions of Binomial Confidence Intervals

N	95% CI
30	31-69
60	37-63
120	40-60

Table 10: Objective 1 -Minimum Detectable Difference in Proportion Responders with 80% Power (N = 50 per group)

Assumed Proportion Responders comparator arm (p_c)	Minimum detectable difference in response rate ($p_c - p_e$)
0.50	0.27
0.60	0.27
0.70	0.27
0.80	0.26
0.90	0.22

Table 11: Objective 2 - Minimum Detectable Difference in Proportion Responders with 80% Power

Assumed Proportion Responders comparator arm (p_c)	Minimum detectable decrease in response rate ($p_c - p_e$)
0.40	0.23
0.50	0.24
0.60	0.25
0.70	0.25
0.80	0.23
0.90	0.20

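### The N=120 row of the precision table should read 41-59, not 40-60, and the table shows enrolled sizes without saying so, although its stated purpose is immunogenicity precision

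*Protocol*

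**What the plan says.** Protocol Section 11.4.3 introduces Table 4 by noting that "Binomial confidence intervals (CI) are widest (have the least precision) when the response rate is 50" per cent. It then says that the table "is presented to indicate the worst-case scenario for precision of observed exact (Clopper-Pearson) binomial confidence intervals". The rows are N = 30 (31-69), N = 60 (37-63) and N = 120 (40-60). The SAP prints the same three rows under "Table 9: Precisions of Binomial Confidence Intervals". Neither table names an endpoint or an analysis population.

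The three Ns are those of the safety table just above (Table 3), where they are explained as being "for a single treatment arm (N = 30 or 60), and for all subjects receiving AS03-adjuvanted 2017 H7N9 IIV (N = 120"). They are enrolled numbers. Section 11.4.2 says "A total of N=60 in Groups 1-2, and N = 30 in Group 3 will be enrolled and randomized".

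Two other places bear on what the table is for. Section 11.2 says that Section 11.4.3 discusses the testing of selected hypotheses, "along with the probability of observing safety outcomes and the precision of immunogenicity outcomes". Section 11.4.2 allows for a loss of at most 15% before the Day 64 visit and concludes that "this will ensure at least N=50 in Groups 1-2 and N=25 in Group 3 are available for the primary immunogenicity analysis". Tables 5 and 6 are built on those reduced sizes, with 50 per group for Objective 1 and 50 against 75 for Objective 2.

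**The concern.** There are two separate matters. First, the N=120 row does not follow from the method named for the table. Second, Section 11.2 presents the precision figures as describing immunogenicity outcomes, but the table uses enrolled sizes, while the sample-size text and the detectable-difference tables plan on smaller numbers for the primary immunogenicity analysis.

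The trial says that it is not designed around a formal null hypothesis and that it aims at meaningful estimates of the immune response. Estimation precision is therefore part of its stated justification, and this table is where the precision of a single proportion is set out. A reader who takes 37-63 or 31-69 as the worst case for a seroconversion rate would be using a sample size larger than the minimum the protocol itself plans for.

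**Working it through.** **Inputs.** Method: exact Clopper-Pearson, two-sided 95%, observed rate 50% (Protocol 11.4.3). Sizes: 30, 60 and 120 (Table 4); minimum immunogenicity sizes 50 and 25 (Protocol 11.4.2).

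**Formula.** For x responders out of N, lower limit = 0.025 quantile of Beta(x, N − x + 1); upper limit = 0.975 quantile of Beta(x + 1, N − x).

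**Step 1: the printed rows.**

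| x/N | Exact 95% CI | Rounded | Printed |
|---|---|---|---|
| 15/30 | 31.30-68.70 | 31-69 | 31-69 |
| 30/60 | 36.81-63.19 | 37-63 | 37-63 |
| 60/120 | 40.74-59.26 | 41-59 | 40-60 |

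The first two rows reproduce, which confirms the method and the rounding to the nearest whole per cent. The third does not.

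**Step 2: could another convention give 40-60 at N=120?** For 60/120, Wald gives 41.05-58.95, Wald with continuity correction 40.64-59.36, Wilson and Agresti-Coull 41.19-58.81, and mid-P 41.11-58.89. All round to 41-59. One responder either way does not help: 59/120 rounds to 40-58 and 61/120 to 42-60. Rounding outward would turn 40.74-59.26 into 40-60, but it would also turn the N=60 row into 36-64, which is not what is printed. No single rounding rule fits all three rows.

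**Step 3: size of the error.** Lower limit: 40.74 − 40 = 0.74 points. Upper limit: 60 − 59.26 = 0.74 points. The printed interval is too wide, so the error is conservative.

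**Step 4: the minimum immunogenicity sizes.** The protocol's 15% loss gives 60 × 0.85 = 51 and 30 × 0.85 = 25.5, in line with its stated minimums of 50 and 25.

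| x/N | Exact 95% CI | Rounded | Half-width |
|---|---|---|---|
| 25/50 | 35.53-64.47 | 36-64 | 14.5 |
| 12/25 | 27.80-68.69 | 28-69 | 20.4 |
| 13/25 | 31.31-72.20 | 31-72 | 20.4 |

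A rate of exactly 50% is impossible with 25 subjects, so the two nearest counts are shown. For comparison, the half-widths are (63.19 − 36.81)/2 = 13.2 at N=60 and (68.70 − 31.30)/2 = 18.7 at N=30. Moving to the minimum sizes therefore adds about 14.47 − 13.19 = 1.3 points for Groups 1 and 2, and 20.45 − 18.70 = 1.8 points for Group 3.

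**The case against.** The strongest reply is that little is at stake. One row of three is off in its last digit, in the safe direction, and nothing else in either document is calculated from it. That stands, and it sets the severity.

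On the sizes, the reply is that enrolled numbers are legitimate. Exact intervals are also planned for solicited and unsolicited adverse event proportions (Protocol 11.6.2; SAP 9.3.1), and for the Safety population 30, 60 and 120 are the right Ns. Sections 11.4.2 and Tables 5 and 6 already disclose the smaller numbers. This also stands: the use of enrolled N is a gap in labelling and consistency, not a miscalculation. It does not remove the gap, because Section 11.2 ties the precision figures to immunogenicity and the table says nothing to the contrary.

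Three stronger readings are tempting, and the documents do not support them.

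- A reader might infer that the N=120 row is really the interval for N=100, that is, two groups of 50. N=100 does give 39.83-60.17, but other sizes also print as 40-60, for example N=102 (39.93-60.07), which is 120 × 0.85. The documents do not say how the row was calculated, so its origin cannot be settled.
- A reader might infer that only 50 and 25 subjects will be analysed. Section 11.4.2 says at least 50 and 25 under a loss of up to 15%, so these are minimums. It first describes that 15% for the per protocol analysis of post dose 3 assessments. The SAP's primary immunogenicity population is mITT (Section 8.1), the seasonal-strain endpoints fall at Day 22, and Group 3 has no later dose to miss. Actual numbers may be closer to 60 and 30.
- A reader might infer that the table is too narrow for every immunogenicity estimate. It is a worst case at 50%. At N=50, 40/50 has a half-width of 11.8 and 45/50 one of 9.2, both below the 13.2 printed for N=60. At N=25, 20/25 has 16.9, below the 18.7 for N=30.

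**Conclusion.** The N=120 row in protocol Table 4 and SAP Table 9 is wrong under its stated method and should read 41-59. This rests only on inputs that the protocol states, plus rounding to whole per cents as the other two rows do. The error is 0.74 points per limit and conservative. The rows for 30 and 60 are correct for the N they state.

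Separately, the table does not match the purpose given for it in Section 11.2. If it is read as immunogenicity precision, its worst case is understated by about 1.3 points in half-width for Groups 1 and 2 and 1.8 points for Group 3. That holds at the protocol's minimum numbers and for rates near 50%, not in general. No sample size, power or analysis is affected. Minor severity.

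**What to change.** In protocol Table 4 and SAP Table 9:

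1. Change the N=120 row from 40-60 to 41-59.
2. Label the 30, 60 and 120 rows as enrolled sizes, applicable to safety proportions.
3. Add rows for the minimum immunogenicity sizes: 50 (36-64) and 25 (28-69 for 12/25, or 31-72 for 13/25).

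Rows for pooled sizes of 75 or 100 are not needed, because immunogenicity intervals are reported by treatment arm (Protocol 11.6.3; SAP Section 8).

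The cost is one corrected cell, a label and two added sizes in each document. The design, sample size and analyses do not change. The stated immunogenicity precision becomes slightly less favourable.

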11.5 Planned Interim Analyses

Interim analyses will only be used to terminate this trial in the event that unanticipated safety events deemed to be of sufficient concern require such action by the sponsor. These assessments will not be made on the basis of testing a formal statistical hypothesis; therefore, p-value adjustment will not be made to any analyses. A DSMB will be convened by DMID to review study progress and participant, clinical, safety, reactogenicity and immunogenicity data as described in [Section 9.6.2](#).

No interim analysis of immunogenicity is planned, however, a preliminary report of safety and immunogenicity data through Day 64 will be prepared as described in [Section 11.6](#); though this report will be released while subjects remain in the trial for long-term safety and immunogenicity follow-up, it will be considered the final analysis of these data.

Emergent public health needs may dictate additional interim safety, reactogenicity, and/or immunogenicity analyses be performed on available information at any time during the trial. If this occurs, immunogenicity data will be analyzed as results are available from the central immunogenicity laboratory.

11.5.1 Interim Safety Review

An interim safety review may include enrollment and demographic information, medical history, concomitant medications, physical assessments, clinical laboratory values, dosing compliance, and solicited and unsolicited AE/SAEs. Additional data may be requested by the DSMB, and interim statistical reports may be generated as deemed necessary and appropriate by DMID. The DSMB may receive data in aggregate and presented by treatment arm, including expected and observed rates of the expected AEs. The DSMB will review grouped data in the closed session only. The DSMB will meet and review this data at scheduled time points or ad hoc as needed during this trial as defined in the DSMB charter. As an outcome of each review/meeting, the DSMB will make a recommendation as to the advisability of proceeding with study vaccinations (as applicable), and to continue, modify, or terminate this trial.

Additionally, this trial will be monitored to determine if any of the halting rules described in [Section 9.5](#) are met.

11.5.2 Interim Immunogenicity Review

No interim immunogenicity analysis is planned. Should emergent public health needs dictate immunogenicity review, immune responses will be summarized in terms of strain-specific 2017 A/H7N9 and IIV4 HAI and Neut antibody titers for subjects that receive sequential or simultaneous administration of AS03-adjuvanted 2017 H7N9 IIV and seasonal IIV4. It is anticipated that all analyses will be carried out in parallel for both assays, but reports may be prepared separately for HAI and Neuts if results are available on different timelines. Interim analyses will focus on rates of titers $\geq 1:40$, seroconversion (defined as either a pre-vaccination titer $< 1:10$ and a post-vaccination titer $\geq 1:40$ or a pre-vaccination titer $\geq 1:10$ and a minimum four-fold rise in post-vaccination titer) and GMTs, along with corresponding 95% CIs. No formal hypothesis testing will be included in the interim analysis, and interim results will not have impact on conduct of this trial.

Any immunogenicity reports would be provided by the SDCC to the DMID Scientific Lead and Clinical Project manager, and the DSMB. Reports will include data summarized by treatment arm.

11.6 Final Analysis Plan

Clinical, safety, and reactogenicity data through approximately 21 days after the third study vaccination will represent the primary clinical database for this trial. Once the last subject completes the visit that occurs approximately 21 days after the third study vaccination, the primary clinical database will be cleaned, monitored, and locked. Analyses of safety, reactogenicity, and available immunogenicity (HAI and Neut antibody assays through Day 64) data by treatment arm are planned. A preliminary report will be prepared by the SDCC after the primary clinical database is locked and all HAI and Neut data for the 2017 H7N9 vaccine strain and all IIV4 strains are received through 21 days after the last study vaccination is received. These analyses may be made available to the sponsor for planning subsequent trials and to the lead principal investigator for publication. These analyses will not be used to make any decisions concerning the conduct of this trial. All analyses of data included in the preliminary report for early release will be considered the final analysis of these data, and also included in the final clinical study report (CSR).

Analysis of exploratory immunogenicity endpoints may be performed and released as the data are available from the research laboratories. Any such analyses would be considered the final analysis for the endpoint, and included in the CSR. The final CSR will be completed after the last subject's last visit is completed, and the final clinical database including all long-term safety follow-up data is cleaned, monitored and locked. Additional exploratory immunogenicity endpoint data not available at the time of CSR preparation may be included in an addendum to the CSR.

A formal statistical analysis plan (SAP) will be developed and finalized prior the primary clinical database lock, which defines the analyses to be included in the Preliminary report, and the final CSR.

11.6.1 Analysis Populations

The Safety Analysis population includes all subjects who received at least one dose of study vaccine.

The modified intent-to-treat (mITT) population includes all subjects who received at least one dose of study vaccine and contributed both pre- and at least one post-study vaccination venous blood samples for immunogenicity testing (HAI or Neut antibody assays) for which valid results

were reported. For analyses using the mITT population, subjects in Group 2 who discontinue treatment after receiving the single IIV4 dose (Dose 1) but prior to receiving the first dose of the H7N9 vaccine (Dose 2) will be analyzed with group 3. All other subjects will be grouped based on randomized treatment arm.

The per protocol (PP) population includes all subjects in the mITT subset with the following exclusions:

- Data from all available visits for subjects found to be ineligible at baseline.
- Data from all visits subsequent to major protocol deviations, such as:
 - Second or third study vaccination not received,
 - Second or third study vaccination received out of window,
 - Receipt of non-study licensed live vaccine within 30 days before or after each study vaccination,
 - Receipt of non-study licensed inactivated vaccine within 14 days before or after each study vaccination,
 - Receipt of immunosuppressive therapy (e.g., corticosteroids) within 30 days before or after each study vaccination.
- Data from any visit that occurs substantially out of window.

For analyses using the PP population, subjects will be grouped based on study vaccinations received.

11.6.2 Safety Data

Summaries and analysis of safety data will be presented for the Safety Analysis Population. All summaries and analyses will be presented for all subjects.

Solicited AEs will be summarized by severity for each day after each study vaccination (Days 1-8 post each study vaccination) and as the maximum severity over all 8 days. Additionally, solicited AEs will be analyzed by taking the most severe response over the follow-up period, dichotomizing into a binary variable (none versus mild, moderate, or severe) and using standard techniques, such as exact confidence intervals, to summarize the proportion of subjects reporting each symptom, any injection site symptom, and any systemic symptom. Summaries of solicited AEs will be presented separately for each study vaccination as well as overall study vaccinations by treatment arm. The proportion of subjects reporting symptoms may be compared between

treatment arms using Chi-square or Fisher's exact test. The proportion of subjects reporting solicited symptoms between the different study vaccinations (i.e., first vs. second, first vs. third, second vs. third, as applicable within each study group) will be compared using McNemar's test.

Unsolicited AEs will be coded by Medical Dictionary for Regulatory Activities (MedDRA®) for preferred term and system organ class (SOC). The numbers of SAEs and MAAEs, including NOCMCs and PIMMCs, are likely to be small in this trial and will be reported by detailed listings showing the event description, MedDRA® preferred term and SOC, relevant dates (study vaccinations and AEs), severity, relatedness, and outcome for each event. Non-serious unsolicited AEs will be summarized as number and percentage of subjects reporting at least one event in each MedDRA® preferred term and SOC, cross tabulated by severity and relationship to study product. Additionally, the proportion of subjects and exact 95% CIs of AEs in aggregate and by MedDRA® categories will be computed.

Clinical laboratory data will be summarized by severity for each visit and as the maximum over all post-study vaccination visits. Graphical presentations may include box plots.

